##### **5.8.1 2nd FMT Administration**

Patients who initially respond to but subsequently progress will be offered a second FMT administration at the time of confirmed progression (RECIST v1.1) at the discretion of the Principal Investigator if no cancer treatment was administered since the last dose of pembrolizumab, the subject meets the safety parameters listed in the Inclusion/Exclusion criteria, and the trial is open. Patients will be required to resign informed consent.

#### **5.9 Subject Withdrawal/Discontinuation Criteria**

Subjects may withdraw consent at any time for any reason or be dropped from the trial at the discretion of the investigator should any untoward effect occur. In addition, a subject may be withdrawn by the investigator or the Sponsor if enrollment into the trial is inappropriate, the trial plan is violated, or for administrative and/or other safety reasons. Specific details regarding discontinuation or withdrawal are provided in Section 7.1.4 – Other Procedures.

A subject must be discontinued from the trial for any of the following reasons:

- The subject or legal representative withdraws consent.
- Confirmed radiographic disease progression

- Unacceptable adverse experiences as described in Section 5.2.1.2
- Intercurrent illness that prevents further administration of treatment
- Investigator's decision to withdraw the subject
- The subject has a confirmed positive serum pregnancy test
- Repeated or serious noncompliance with trial treatment or procedure requirements
- The subject is lost to follow-up
- Completed 24 months of uninterrupted treatment with pembrolizumab or 35 administrations of study medication.

*Note: 24 months of study medication is calculated from the date of first dose. Subjects who stop pembrolizumab after 24 months may be eligible for up to one year of additional study treatment if they progress after stopping study treatment provided they meet the requirements detailed in Section 7.1.5.5*

- Administrative reasons

The End of Treatment and Follow-up visit procedures are listed in Section 6 (Protocol Flow Chart) and Section 7.1.5 (Visit Requirements). After the end of treatment, each subject will be followed for 30 days for adverse event monitoring (serious adverse events will be collected for 90 days after the end of treatment as described in Section 7.2.3.1). Subjects who discontinue for reasons other than PD will have post-treatment follow-up for disease status until disease progression, initiating a non-study cancer treatment, withdrawing consent or becoming lost to follow-up. After documented disease progression each subject will be followed for overall survival until death, withdrawal of consent, or the end of the study, whichever occurs first.

## **5.10 Subject Replacement Strategy**

Patients are deemed evaluable for safety if they were screened and received FMT and at least one dose of pembrolizumab. Patients are deemed evaluable for efficacy if they completed screening and received FMT/pembrolizumab and 1st re-staging scan. Patients who drop out of the study for reasons related to disease progression **prior to 1st re-staging scan** may be replaced.

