## **8.5. Analysis Plan**

### **8.5.1. Decision Rule and Sample Size Justification**

#### **8.5.1.1. Patient Evaluability and Definition of Objective Response**

All patients meeting the eligibility criteria who have signed a consent form and begun pembrolizumab and/or FMT will be considered evaluable for estimation of the response probability. For evaluable patients, objective response will be assessed by RECIST 1.1.

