#### **8.5.1.2. Decision Rule:**

Based on prior data on response rates in this patient population, the largest ORR where the proposed treatment would be considered unpromising in this population is 5%. The smallest success proportion that would warrant further subsequent studies with the proposed treatment in this patient population is 25%. The following design is based on Simon's minimax two-stage study design and uses to test the null hypothesis that the true success rate in each patient population is at most 5%.

In Stage 1: Enter 13 evaluable patients and follow for at least 12 weeks. If 0 patients have a confirmed response in this timeframe, we will consider this early evidence that this treatment regimen is not sufficiently active in this patient population. If 1 or more patients have a response, then accrual will continue in the second stage of this trial.

In Stage 2: Enter an additional 7 evaluable patients to the trial. If 2 or fewer successes are observed in the 20 evaluable patients, we will consider this sufficient evidence that this treatment is not sufficiently effective in this patient population. If 3 or more successes are observed in the first 20 evaluable patients, then this treatment will be considered promising in this patient population and will be evaluated further in future studies.

Power and Significance Level: Assuming that the number of successes is binomially distributed, this decision rule has a significance level of 0.07; i.e., there is a 7% chance of finding the drug to be effective when it truly is not. This decision rule has 90% power to detect an effective treatment given that the true response rate is at least 25% using this treatment.

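### Section 5.10 removes and allows replacement of patients who progress before the first scan, which conflicts with Section 8.5.1.1 and, where applied, inflates the ORR and the 7% type I error

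*Combined protocol and SAP*

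**What the plan says.** Section 5.10 (Subject Replacement Strategy) sets the efficacy set: "Patients are deemed evaluable for efficacy if they completed screening and received FMT/pembrolizumab and" a first restaging scan. It then says that "Patients who drop out of the study for reasons related to disease progression" before that scan may be replaced.

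Section 8.5.1.1 defines the set for estimating the response probability differently: "All patients meeting the eligibility criteria who have signed a consent form and begun pembrolizumab and/or FMT will be considered evaluable". It has no scan condition.

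The decision rule in Section 8.5.1.2 is written in evaluable patients throughout. Stage 1 reads "Enter 13 evaluable patients and follow for at least 12 weeks", with futility declared "If 0 patients have a confirmed response in this timeframe". At the end, "If 3 or more successes are observed in the first 20 evaluable patients, then this treatment will be considered promising". Section 8.5.2 divides responses by the total number of evaluable patients to obtain the ORR. No text says which definition governs, and Section 8 contains no replacement rule.

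**The concern.** A patient who leaves because of progression before the first scan has failed treatment. Under Section 8.5.1.1 that patient stays in the denominator as a non-responder. Under Section 5.10 the patient leaves the efficacy set, and another patient may take the place, with a fresh chance of responding. That is selection on the outcome, and it can act in only one direction.

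The window is long. The study calendar notes put the first restaging after four cycles, at 12 weeks, and entrants have already progressed on PD-1 therapy. Replacement is also discretionary in an open-label trial, so whether a known failure counts would be decided case by case without stated criteria.

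Three things are at stake: the reported ORR, the stage 1 futility gate and the final call at 3 of 20. With a threshold of three responses, one or two replaced places can change the verdict.

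**Working it through.** **Inputs (Section 8.5.1.2).** Null ORR: "the largest ORR where the proposed treatment would be considered unpromising in this population is 5" per cent. Target: "The smallest success proportion that would warrant further subsequent studies with the proposed treatment in this patient population is 25" per cent. Stage 1 has 13 patients and stops at 0 responses. Stage 2 adds 7, and success is at least 3 of 20. Stated significance level 0.07, stated power 90%.

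**Step 1: reproduce the plan's figures.** With X1 ~ Bin(13, p) and X2 ~ Bin(7, p), independent:

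P(declare promising) = Σ over x = 1 to 13 of P(X1 = x) × P(X2 ≥ 3 − x)

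- p = 0.05: 0.3512 × 0.0444 (x = 1) + 0.1109 × 0.3017 (x = 2) + 0.0245 (x ≥ 3) = 0.0736, which is the stated 0.07.
- p = 0.25: 0.1029 × 0.5551 + 0.2059 × 0.8665 + 0.6674 = 0.903, which is the stated 90%.
- Chance of stopping after stage 1 under the null: 0.95^13 = 0.513.

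These figures hold when p is the response rate among the patients actually counted. Under Section 8.5.1.1 those are all treated patients.

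**Step 2: apply Section 5.10.** Let d be the share of treated patients who progress out before the first scan, all of them non-responders and all replaced. The documents do not give d, so a range is shown. If the ORR among all treated patients is p, the rate among counted patients is p/(1 − d). Putting 0.05/(1 − d) into the Step 1 formula gives:

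| d (assumed) | Apparent ORR when the true ORR is 5% | Type I error | Stage 1 stop probability under the null | Expected treated for 20 counted, 20/(1 − d) |
|---|---|---|---|---|
| 0 | 5.0% | 0.074 | 0.513 | 20.0 |
| 5% | 5.3% | 0.083 | 0.495 | 21.1 |
| 10% | 5.6% | 0.094 | 0.476 | 22.2 |
| 20% | 6.25% | 0.123 | 0.432 | 25.0 |
| 30% | 7.1% | 0.164 | 0.382 | 28.6 |

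Worked row, d = 20%: the rate is 0.05/0.80 = 0.0625, and 0.3745 × 0.0665 + 0.1498 × 0.3635 + 0.0435 = 0.123. Type I error first exceeds 0.10 at d of about 12.4%.

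**Step 3: effect on the reported estimate.** At d = 20%, 20 counted patients correspond to 25 treated. Three responses would be reported as 3/20 = 15.0% (exact 95% CI 3.2% to 37.9%). Among all treated patients the figure is 3/25 = 12.0% (2.5% to 31.2%).

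**The case against.** The strongest reply is that Section 8.5.1.1 governs. It opens the decision-rule section, it says who counts toward the response probability, and the term evaluable in Sections 8.5.1.2 and 8.5.2 follows from it. The Trial Summary's total of 20 leaves no room for extra treated patients. On that reading the 7% is correct. This is fair as a reading, but the protocol does not say so, and Section 5.10 defines evaluability for efficacy in express terms. A site following Section 5.10 would be following the protocol.

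Second, the size is uncertain. Replacement is optional, and d could be small:
- Section 5.1.2 excludes rapidly progressing and highly symptomatic patients, and Section 5.1.1 requires ECOG 0 or 1.
- Section 7.1.2.6 asks for progression on two assessments at least 4 weeks apart, so a patient who leaves by that route has been scanned.
- Section 5.10 does not say that the first restaging scan must be the week-12 one, so an early unscheduled scan might keep a progressor in the set.

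These points limit the magnitude. They do not remove the conflict or change the direction of the bias.

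Third, the 5% and 25% rates might have been meant per scanned patient. The 7% would then hold for that narrower set. Counting unscanned patients as failures would lower power, from 0.903 to 0.854 at d = 10% or 0.786 at d = 20% (same formula with p = 0.25(1 − d)). Nothing in the documents supports that reading: Section 8.5.1.2 sets both rates for the patient population, and Section 8.5.1.1 counts everyone who starts treatment.

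**Conclusion.** The concern holds. The plan has two definitions of the primary-endpoint denominator, does not rank them, and one of them discards treatment failures.

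The 7% is computed correctly and stands if all treated patients are counted. It fails to the extent that Section 5.10 is applied and patients progress out before the first scan. If every such patient is replaced, type I error runs from 0.083 at d = 5% to 0.164 at d = 30%, the expected ORR rises by a factor of 1/(1 − d), and the stage 1 gate becomes easier to pass. The size rests on three assumptions: the value of d, replacement in every case, and rates of 5% and 25% that refer to all treated patients. The direction depends only on early progressors being non-responders.

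This must be settled before outcomes are known, because it affects the stage 1 decision, the final decision and the reported ORR together.

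**What to change.** Use the Section 8.5.1.1 definition in both sections:

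- Every eligible, consented patient who begins FMT and/or pembrolizumab counts toward the 13 and the 20, and in the ORR denominator.
- A treated patient with no post-baseline scan counts as a non-responder, whether the reason is progression, death, toxicity or withdrawal. Section 5.10 as written also drops the toxicity and withdrawal cases from the efficacy set, although it names only progression dropouts as replaceable.
- Delete replacement for progression from Section 5.10. Allow replacement only for patients who never start study treatment.
- An ORR among scanned patients may be reported as a labelled sensitivity analysis, with no role in the decision rule.

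This keeps the operating characteristics at 0.0736 and 0.903 with 20 patients. The cost is protocol and SAP wording, and a reported ORR that may be slightly lower. If the sponsor did intend 25% as a rate per scanned patient, that should be stated and the power recalculated, since it would fall as shown under the objection.

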## **5.11 Clinical Criteria for Early Trial Termination**

Early trial termination will be the result of the criteria specified below:

1. Quality or quantity of data recording is inaccurate or incomplete
2. Poor adherence to protocol and regulatory requirements

3. Incidence or severity of adverse drug reaction in this or other studies indicates a potential health hazard to subjects
4. Plans to modify or discontinue the development of the FMT infusate

**Product:** Pembrolizumab  
**Protocol/Amendment No.:**

Trial Period:	Screening Phase	Treatment Cycles a								End of Treatment	Post-Treatment		
		1*	2*	3*	4*	To be repeated beyond 4 cycles					Discontinuation	Safety Follow-up A	Follow Up Visits B
Treatment Cycle/Title:	Study Screening (Visit 1)	5*	6*	7*	8+*								
Scheduling Window (Days):	-28 to -1	± 3	± 3	± 3	± 3	± 3	± 3	± 3	± 3	At time of discontinuation	30 days post discontinuation	Every 12 weeks	Every 12 weeks
Screening labs prior to FMT administration (see Appendix 2)	+												
Laboratory Procedures/Assessments: analysis performed by LOCAL laboratory													
Hematology and serum chemistry E	+	+	+	+	+	+	+	+	+				
Coagulation studies and urinalysis F	+												
Thyroid studies G	+	+		+		+		+					
Efficacy Measurements													
Tumor Imaging H	+				+				+				
CNS Imaging (if not previously performed) *CNS imaging will be incorporated into restaging assessments if prior CNS disease is known/stable H	+*				+				+				
Tumor Biopsies; Archival Tissue Collection; Correlative Studies Blood/Stool													
Tissue Collection (pre-treatment and C4; biopsy at progression is optional)	+				+								
Correlative studies (blood) I	+	+	+	+	+	+	+	+	+(q12)			+	
Correlative studies (stool) J	+	+	+	+	+	+	+	+	+(q6)			+	
Dietary questionnaire (Appendix 3) K	+	+	+	+	+	+	+	+	+(q12)				

**Product:** Pembrolizumab  

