#### 5.2.1.2 Dose Modification (Escalation/Titration/Other)

Adverse events (both non-serious and serious) associated with pembrolizumab exposure may represent an immunologic etiology. These adverse events may occur shortly after the first dose or several months after the last dose of treatment. Pembrolizumab must be withheld for drug-related toxicities and severe or life-threatening AEs as per Table 7-1 (see **Appendix 5: Dose Modifications for Pembrolizumab**).

In case toxicity does not resolve to Grade 0-1 within 12 weeks after last infusion, trial treatment should be discontinued after consultation with the Principle Investigator. With investigator and Sponsor agreement, subjects with a laboratory adverse event still at Grade 2 after 12 weeks may continue treatment in the trial only if asymptomatic and controlled. For information on the management of adverse events, see Section 5.6.1.

Subjects who experience a recurrence of the same severe or life-threatening event at the same grade or greater with re-challenge of pembrolizumab should be discontinued from trial treatment.

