### **5.2.2 Timing of Dose Administration (Pembrolizumab)**

Trial treatment should be administered on Day 1 of each cycle after all procedures/assessments have been completed as detailed on the Trial Flow Chart (**Section 6.0**). Trial treatment may be administered up to 3 days before or after the scheduled Day 1 of each cycle due to administrative reasons. Pembrolizumab will be given on study for 4 cycles (minimum) and up to 8 cycles in patients who are responding (or receiving clinical benefit as assessed by Principle Investigator). In patients who continue to respond (or receive clinical benefit), pembrolizumab will be administered by treating investigator(s) until disease progression or up to 2 years from FMT administration (35 cycles total).

All trial treatments will be administered on an outpatient basis.

Pembrolizumab 200 mg will be administered as a 30 minute IV infusion every 3 weeks. Sites should make every effort to target infusion timing to be as close to 30 minutes as possible. However, given the variability of infusion pumps from site to site, a window of -5 minutes and +10 minutes is permitted (i.e., infusion time is 30 minutes: -5 min/+10 min).

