**Protocol/Amendment No.:**

Study Calendar Notes:

A Safety follow up: For all patients (responders and non-responders) at 30 days (+/- 10 days) following cycle 8 pembrolizumab on study.

B Follow up visits: For all responder patients only every 12 weeks (+/- 14 days) following cycle 4 pembrolizumab on study. Will include correlative stool sampling.

C Survival follow up visits: For all patients (responders and non-responders) every 12 weeks (+/- 14 days) following cycle 8 pembrolizumab on study

D Patients self-monitoring: while on study, patients will be provided a memory card and digital thermometer to facilitate the standardized collection of AEs particularly AEs commonly associated with FMT including fever, diarrhea, vomiting, abdominal discomfort, constipation, and flatulence.

E CBC w/diff, Comprehensive Serum Chemistry Panel (allowed within 28 days)

F PT/INR and aPTT; urinalysis; Pregnancy Test; Stool and Blood Screening (allowed within 28 days)

G FT4 and TSH (allowed within 28 days) To be repeated at every odd cycle.

H Restaging imaging will be obtained after 4 cycles of therapy (12 weeks) comprising of CT or PET/CT imaging. Scans will be repeated every 12 weeks. If CNS lesions were present at staging, restaging imaging should include MRI brain or CT head with contrast. If CNS lesions were not present at staging scans, this need not be repeated.

I Correlative laboratory studies will be performed at Screening, during each cycle (Cycles 1-8) and q12 weekly afterwards till EOT.

J Correlative stool studies will be performed at Screening, weekly (Cycles 1-8), and q6 weekly afterwards till EOT.

K Following FMT, dietary history questionnaire (Appendix 3) will be monitored q12 weekly afterwards till EOT.

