#### **7.1.5.4 Post-Treatment Visits**

End of treatment (EOT) is defined as the visit where the decision is made to discontinue the participant from treatment. Evaluations will be performed prior to study discharge, or for participants who are prematurely discontinued, or participants who complete all scheduled cycles of therapy, the EOT visit will be the same as the last scheduled and completed on-treatment visit.

For participants who complete all scheduled cycles of therapy, the EOT visit will be the same as the last scheduled and completed on-treatment visit (eg, Cycle 9 Day 1) and the start of the safety follow-up period. For participants that do not complete all scheduled cycles of therapy, the EOT visit will be the most recent on-treatment visit (with all available safety and response data), does not need to be repeated and will be considered the start of the safety follow-up period.

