##### **7.1.5.4.1 Safety Follow-Up Visit**

The mandatory Safety Follow-Up Visit should be conducted approximately 30 days (+/- 10 days) after the last dose of trial treatment or before the initiation of a new anti-cancer treatment, whichever comes first. All AEs that occur prior to the Safety Follow-Up Visit should be recorded. Subjects with an AE of Grade > 1 will be followed until the resolution of the AE to Grade 0-1 (or baseline) or until the beginning of a new anti-neoplastic therapy, whichever occurs first. SAEs that occur within 90 days of the end of treatment or before initiation of a new anti-cancer treatment should also be followed and recorded. Subjects who are eligible for retreatment with pembrolizumab (as described in Section 7.1.5.5) may have up to two safety follow-up visits, one after the Treatment Period and one after the Second Course Phase.

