## **7.2 Assessing and Recording Adverse Events**

An adverse event is defined as any untoward medical occurrence in a patient or clinical investigation subject administered a pharmaceutical product and which does not necessarily have to have a causal relationship with this treatment. An adverse event can therefore be any unfavorable and unintended sign (including an abnormal laboratory finding, for example), symptom, or disease temporally associated with the use of a medicinal product or protocol-specified procedure, whether or not considered related to the medicinal product or protocol-specified procedure. Any worsening (i.e., any clinically significant adverse change in frequency and/or intensity) of a preexisting condition that is temporally associated with the use pembrolizumab and/or FMT is also an adverse event.

Changes resulting from normal growth and development that do not vary significantly in frequency or severity from expected levels are not to be considered adverse events. Examples of this may include, but are not limited to, teething, typical crying in infants and children and onset of menses or menopause occurring at a physiologically appropriate time.

Adverse events may occur any time during the course of the clinical trial. Progression of the cancer under study is not considered an adverse event.

All adverse events that occur after the consent form is signed but before treatment initiation must be reported by the investigator if they cause the subject to be excluded from the trial, or are the result of a protocol-specified intervention, including but not limited to washout or discontinuation of usual therapy, diet, placebo treatment or a procedure.

From the time of treatment initiation through 30 days following cessation of treatment, all adverse events must be reported by the investigator. Such events will be recorded at each examination on the Adverse Event case report forms/worksheets. The reporting timeframe for adverse events meeting any serious criteria is described in section 7.2.3.1. The investigator will make every attempt to follow all subjects with non-serious adverse events for outcome.

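### No hematology, chemistry or thyroid test is scheduled after the treatment cycles, so silent laboratory toxicity in the 30-day post-treatment window is not systematically ascertained, above all in patients who stop early

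*Combined protocol and SAP*

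**What the plan says.** **Laboratory schedule.** In the flow chart (6.0), "Hematology and serum chemistry" is marked at screening and cycles 1 to 8+. Thyroid tests are marked at screening and cycles 1, 3, 5 and 7, and Note G reads "FT4 and TSH (allowed within 28 days) To be repeated at every odd cycle". Neither row has a mark under Discontinuation, Safety Follow-up or any later column.

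**Order within a visit.** Section 5.2.2: "Trial treatment should be administered on Day 1 of each cycle after all procedures/assessments have been completed".

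**End of treatment.** Under 7.1.5.4, the end-of-treatment (EOT) visit of a patient who does not complete therapy is the most recent on-treatment visit, which "does not need to be repeated and will be considered the start of the safety follow-up period". For completers it is the last scheduled on-treatment visit, with Cycle 9 Day 1 as the example. Section 7.1.4.1 asks at discontinuation for whatever the final visit schedules.

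**Adverse-event window.** Section 5.9: "After the end of treatment, each subject will be followed for 30 days for adverse event monitoring". Section 7.2: "From the time of treatment initiation through 30 days following cessation of treatment, all adverse events must be reported by the investigator". Section 7.2 also counts an abnormal laboratory finding as an adverse event.

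**Safety visit.** Section 7.1.5.4.1 makes it mandatory at 30 (+/- 10) days after the last dose, or before new anti-cancer treatment if that comes first. It names no laboratory test and says: "All AEs that occur prior to the Safety Follow-Up Visit should be recorded". Note A to the flow chart times the same visit from cycle 8.

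**The concern.** Section 4.2.4.1 lists safety/toxicity with objective response as primary, and 8.5.2 tabulates the maximum grade of each toxicity per patient. Hepatic, renal, hematologic and thyroid events are often silent and then appear only in a blood test. The patient memory card (Appendix 4) covers fever and gastrointestinal symptoms, so it would not pick them up.

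The protocol itself expects late events. Of pembrolizumab-associated events, 5.2.1.2 says: "These adverse events may occur shortly after the first dose or several months after the last dose of treatment". Yet the laboratory schedule stops before the last dose is given. A test that is not done can lower a recorded maximum grade but cannot raise it, so any error runs one way. At stake are the completeness of the toxicity tables and, for the individual patient, detection of a silent event after treatment has stopped.

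**Working it through.** The plan gives no figure to reproduce here. The check has two parts: whether any section schedules a test after the last dose, and how long the gap is.

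**1. Does any section schedule a test?**

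| Source | What it contributes |
|---|---|
| Flow chart, laboratory rows | 13 columns: screening, 8 cycle columns, discontinuation and 3 post-treatment columns. The last 4 are blank in both rows |
| 5.2.2 | The draw on the last dosing day precedes that dose |
| 7.1.4.1 | Repeats what the final visit schedules; the Discontinuation column holds no laboratory test |
| 7.1.5.4, early stoppers | EOT is the last on-treatment visit, so no new draw |
| 7.1.5.4, completers | A Cycle 9 Day 1 visit, with the 8+ column and the odd-cycle rule in Note G, could bring both tests |
| 7.1.5.4.1 | Mandatory visit, no laboratory test named |

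The correlative blood and stool rows do carry a mark in the follow-up visit column, so the chart can show post-treatment entries.

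**2. How long is the gap?**

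Inputs: 3-week cycles (Table 5.2-1), with dosing windows ignored; a 30-day adverse-event window (5.9, 7.2), counted from the last dose.

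- Day of dose *k*: d = 21(*k* − 1) + 1. The window ends on day d + 30.
- Last hematology/chemistry: day d, before the dose. Gap = (d + 30) − d = 30 days for every *k*.
- Last thyroid test: day d if *k* is odd, giving a gap of 30 days; day d − 21 if *k* is even, giving 30 + 21 = 51 days.

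| Last dose | Day | Window ends | Chemistry gap | Last thyroid test | Thyroid gap |
|---|---|---|---|---|---|
| Cycle 4 | 64 | 94 | 30 (30/94 = 32%) | 43 | 51 (51/94 = 54%) |
| Cycle 5 | 85 | 115 | 30 (30/115 = 26%) | 85 | 30 (26%) |
| Cycle 6 | 106 | 136 | 30 (30/136 = 22%) | 85 | 51 (51/136 = 37.5%) |
| Cycle 8, no Cycle 9 visit | 148 | 178 | 30 (30/178 = 17%) | 127 | 51 (51/178 = 29%) |

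Percentages are shares of the time from day 1 to the end of the window, taken as the window-end day number. If a completer attends Cycle 9 Day 1 (day 8 × 21 + 1 = 169) with laboratory tests, both are drawn 169 − 148 = 21 days after the last dose.

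**3. The visit window.** The earliest permitted safety visit is 30 − 10 = day 20. Section 7.1.5.4.1 asks for events before that visit, whereas 5.9 and 7.2 run to day 30. That leaves up to 10 days covered by the reporting duty but by no scheduled visit.

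**The case against.** The strongest reply is that an unscheduled test is still a test. Section 7.1 allows procedures at unscheduled times when clinically necessary. The hepatic Event of Clinical Interest (7.2.3.2) accepts unscheduled results. Known events above Grade 1 are followed to resolution, baseline or new therapy (7.1.5.4.1). All of this stands. A reader might infer that laboratory toxicity of the last dose goes unseen, or that about a quarter of silent events in four-dose patients (one dose of four) are never observed. The documents do not support either statement. The second needs a constant risk per dose and no unscheduled testing at all, and neither is given.

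Nor is stopping after four doses shown to be typical. Section 7.1.2.6 requires progression on two assessments at least 4 weeks apart with pembrolizumab continued between them. A patient progressing at first restaging would usually reach cycle 5 and possibly cycle 6. Four doses remain possible for toxicity, withdrawal or investigator decision.

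No decision rule turns on these events. Toxicity is described in frequency tables without a test. The dose-limiting toxicity window is four weeks after FMT (8.3), and the cycle 2 draw on day 22 falls inside it. The stopping rule in 8.4 concerns deaths.

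On the visit window, the duty to report to day 30 holds whatever the visit date, so an early visit weakens the means of collection and not the obligation.

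One caveat concerns the chart. In the text available, its clinical-procedure rows are missing and no surviving row has a mark under Discontinuation or Safety Follow-up, so those two columns have no positive control. The laboratory rows themselves appear complete.

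What survives is that testing at discretion is not systematic ascertainment: a silent event gives the investigator no prompt to test.

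**Conclusion.** The point holds as a gap in scheduled ascertainment. For a patient who stops early, nothing in the plan schedules a hematology, chemistry or thyroid test after the last dose. The gap to the end of the adverse-event window is 30 days for hematology and chemistry, and 30 days (odd last cycle) or 51 days (even last cycle) for thyroid. For completers it depends on whether a Cycle 9 Day 1 visit is held with its laboratory tests, which 7.1.5.4 suggests only by example.

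The toxicity record can therefore err only downward. How many events would be missed cannot be derived from the documents. For scale, one patient is 1/20 = 5 percentage points of a rate in the planned 20. The response analysis and the two-stage rule are unaffected.

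The conclusion assumes that the 30 days run from the last dose, that visits fall on nominal days, and that the blank cells in the laboratory rows are as the sponsor wrote them.

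The day-20 safety visit is a separate and smaller inconsistency with the 30-day window in 5.9 and 7.2.

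**What to change.** 1. In the flow chart, mark hematology and serum chemistry (Note E) and FT4/TSH (Note G) in the Safety Follow-up column.
2. Reconcile Note A, which times the safety visit from cycle 8, with 7.1.5.4.1, which times it from the last dose, so that patients who stop early are covered. Without this, the new marks could miss the patients for whom the gap is clearest.
3. Reconcile the Cycle 9 Day 1 example in 7.1.5.4 with the blank Discontinuation column, stating whether that visit includes laboratory tests.
4. In Note A and 7.1.5.4.1, change the visit window from 30 (+/- 10) to 30 (+10) days, keeping the existing exception for a visit before new anti-cancer therapy. The visit then closes the window stated in 5.9 and 7.2.

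The cost is an amendment to the chart and wording, and one routine local blood draw per patient at a visit already required. The reported laboratory toxicity rate may rise slightly. A single draw will still miss a silent event that resolves before the visit.
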